- 3) To compare the result between group 1 and group 2,so as to find out the possible benefits in the precise therapy group(group 1);
- 4) To promote the appliance of 3-D imaging techniques for patients with CTEPH, and establish a standard precise PEA strategy guided by enhanced CT scanning and pulmonary angiography,in order to further improve the surgical result for patients with CTEPH,especially for patients with peripheral changes.

3 Design and Method

1) General design

This is a randomized single-blinded controlled study, 72 cases of patients are expected to be enrolled into this study, and randomized into 2 groups. The endpoint of these 2 groups will be compared to determine the efficiency of the appliance of 3-D imaging techniques for PEA procedures.

2) Clinical data collection process:

Pre-operative period: From admission to the moment before surgeries. Basic clinical information including the patients' age, gender, symptoms, clinical diagnosis, WHO classes, disease history et al. Blood test such as the thrombus forming tendency test, blood coagulation function test, coagulation factor activity test and N-terminal B-type natriuretic peptide (NT-proBNP) et al were collected. Other examinations included CT scanning, MRI, CPET, RHC and pulmonary angiography, pulmonary nuclide perfusion imaging, respiratory function test and UCG et al. The major parameters of these examinations are collected.

[figure not shown]
Operation period: The RHC result immediately before and after PEA surgeries are documented, the anesthesia record and CPB record, surgical specimen pathological record, intra-operative cerebral oxygen saturation data will be collected;

Post-operative period before discharge: Pulmonary nuclide perfusion imaging, CT scanning and UCG should be done in this period.

Follow-up period: A routine 3-, 6-, 12-, 24 months follow-up will be done, the follow-up contents include the measuring of NT-pro BNP, UCG, CPET, CT scanning, RHC, pulmonary angiography, pulmonary perfusion imaging, MRI and RHC. Among which the CPET, MRI, RHC and pulmonary angiography should be done after 6 months after surgeries. All the redo examinations could be done in any follow-up period, but at least 1 time of these examinations should be done in the whole follow-up period, and the follow-up time should be recorded.

[figure not shown]
3) CT Imaging assessment:

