① According to the imaging examinations before surgeries, the location of each occluded pulmonary segment and their shape were identified and the affected pulmonary segments were divided into 3 types: i) segments that are easy to reach; ii) segments that are hard to reach (seen in the picture below), and severely occluded; iii) segments that are hard to reach but slightly occluded;

[figure not shown]
An example of segments hard to reach. As shown in the picture, the shape of LA5 of this patient is exactly perpendicular to the surgical direction, which lead to a fact that the embolism in this segment very hard to strip. For the subsegment LA8a+b, it is too far away from the proximal artery, which is very hard to reach at surgeries.

② All the occlusion severity of each segment and narrow severity of each segment is assessed with CT scanning;

An example of constructed CT imaging of the pulmonary segment: A demonstration of the anatomic structure of pulmonary segments. White arrow: not severely narrow segment of RA9; Red arrow: severely narrow segment of LA4.

4) Research process:seen in the picture below.

4 Eligibility/intervention information/Arm information

Eligibility:

Patients were **eligible** if they had met all the following conditions:

[figure not shown]
- 1) Diagnosed with CTEPH by pulmonary angiography and RHC examinations;
- 2) The location of the embolism can be reached in surgery;
- 3) Whether or not combined with auto-immune diseases;

Patients were **not eligible** if they had met any one of the following conditions:

- 1) history of other severe diseases and surgical therapy is contraindicated;
- 2) Unwillingness to participate or without informed consent;
- 3) acute pulmonary embolism;
- 4) pulmonary sarcoma;
- 5) Patients with mitral valve diseases, or other conditions that may lead to cardiogenic pulmonary hypertension;
- 6) Pulmonary hypertension caused by pulmonary arteritis.

Intervention information:

Precised analyzed CT scanning and pulmonary angiography will be done for the patients in the precise therapy group, and the patients in Group 1 will receive PEA procedure with the guide of precise 3-D imaging techniques (seen in the picture below)

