An example of precise therapy process.A,3-D CT constructed images,which can provide the detailed information of each pulmonary segmental shape and their distribution;B,enhanced CT imaging of pulmonary segment,to assess the occluded severity of each pulmonary segment;C:Diagrammatic sketch of pulmonary artery embolism's location,red marked font refer to pulmonary segments with occupying changes;as shown in the picture,the RA4,RA2,RA5 is completely occluded,other affected segment is partially occluded.D.Surgical specimen;the occupying lesions in each pulmonary segment is stripped according to the embolism location identified by high-resolution CT scanning(seen in picture C);E,clearly opened pulmonary segment entrance after precise stripping therapy.

Arm information:All the patients included into this study met the requirements above and randomized into 2 groups:

group 1:precise PEA therapy with the guide of 3-D imaging techniques;

group 2:traditional PEA therapy solely by surgical probe and traditional CT scanning/pulmonary angiography method.

100 cases of randomized group were generated,which consisted of 50 cases of group 1 and 50 cases of group 2, and 100 cases of randomized number was generated paralleled with the randomized group.According to the date of admission of each patients,they are included into the randomized group one by one,any patient met the criteria of the **not eligible** described above will be excluded from this experiment, and all the patients consent to participate in this study will not know their specific group, the chief surgeon can only know the random grouping situation after the patients been admitted into hospital.

5 Outcome measures and time frame

The primary endpoint for assessment of the efficacy was the peri-operative hemodynamic improvement, peri-operative mortality, major complications after surgery, and deaths in the follow-up period.

Secondary endpoint were the measuring values of NT-pro BNP, parameters of MRI, UCG and CPET in the follow-up period, the CT scoring changes from baseline to follow-up period, and WHO function classes in the follow-up period, as well as disease directly associated cost (average cost) in the follow-up period.

6 Statistical Analysis Plan

This is a prospective randomized single-blinded controlled study, the major endpoint is the hemodynamic improvement after the surgeries.

1) Sample Size:

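### Section 4 ties list entry and the surgeon's possible knowledge of the arm to admission, and no readable rule requires consent and eligibility to be settled first

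*Combined protocol and SAP*

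**What the plan says.** Section 4, Arm information, sets the allocation procedure. It opens with "All the patients included into this study met the requirements above and randomized into 2 groups". The list is described as "100 cases of randomized group were generated,which consisted of 50 cases of group 1 and 50 cases of group 2". Patients then join it as follows: "According to the date of admission of each patients,they are included into the randomized group one by one". The same sentence adds that anyone meeting a not-eligible criterion "described above will be excluded from this experiment", that consenting patients are not told their group, and that "the chief surgeon can only know the random grouping situation after the patients been admitted into hospital".

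The not-eligible criteria in Section 4, Eligibility, include "Unwillingness to participate or without informed consent" as item 2. Item 1 covers other severe disease with surgery contraindicated. Inclusion requires a diagnosis by angiography and RHC, and a lesion that surgery can reach.

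Section 3, Clinical data collection process, starts the pre-operative period at admission and lists CT, RHC and angiography within it. Section 3, item 4, gives the overall sequence only as "Research process:seen in the picture below", and that figure is not shown. The Brief Introduction says that patients are expected to be included with a signed consent form. Section 6 bases the analysis on intention to treat and keeps all randomised patients, whether or not they violate the protocol.

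**The concern.** Allocation protects the comparison only if whoever decides on entry cannot know the next arm, or act on it, until that decision is final. Here admission is the only dated event attached to list entry, and it is the only bar to the chief surgeon knowing the arm. Consent, the eligibility decision and exclusion are all mentioned, but none is dated against either event.

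Three features make this more than a drafting gap:

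- The examinations behind the diagnosis are listed in the period after admission, when the surgeon may already know the arm.
- Some entry judgements leave room for discretion, notably whether surgery is contraindicated and whether the lesion can be reached.
- Section 4 provides the precise CT and angiography analysis for group 1. If eligibility is still open after allocation, the two arms could be judged on different information.

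If exclusion or the seeking of consent depended on the arm, the groups could differ before surgery, and the test of the 8 mmHg difference would lose part of its randomised basis. The plan also does not say when a patient counts as randomised, so the intention-to-treat rule cannot be relied on to close the gap.

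**Working it through.** **Order of events in the readable text**

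| Step | Where | Timing stated |
|---|---|---|
| Entry on the list | Section 4, Arm information | By admission date |
| Surgeon may know the arm | Section 4, Arm information | Not before admission |
| Exclusion | Section 4, Arm information | None |
| Consent | Section 4, exclusion 2; Brief Introduction | Tied to inclusion; not dated against allocation |
| RHC, angiography, CT | Section 3 | From admission to surgery |
| Analysis set | Section 6 | All randomised; moment of randomisation not defined |

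Nothing here places exclusion or consent before the arm may be known.

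**The plan's own figure.** Inputs from Section 6: difference 8 mmHg, SD 12 mmHg, two-sided 5%, power 80%. n per arm = 2 × [(1.960 + 0.842) × 12 / 8]² = 35.3, rounded up to 36. This reproduces the stated 36. Power at 36 per arm is 80.7% by the normal approximation and 79.7% by the exact t-test.

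**Illustration of bias.** The documents give neither an exclusion rate nor a correlation, so both are assumptions. Suppose there is no true effect, 36 patients are analysed per arm and SD is 12. In one arm only, the fraction f with the lowest screening scores is removed, and the screening score has correlation r with the outcome. Then

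shift = 12 × r × φ(z_f) / (1 − f),

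where z_f is the f-quantile of the standard normal distribution and φ its density. For f = 0.20 and r = 0.5: 12 × 0.5 × 0.280 / 0.80 = 2.10 mmHg. Type I error comes from 200,000 simulated two-sided t-tests per scenario.

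| Removed from one arm | Shift, r = 0.3 / 0.5 (mmHg) | Share of 8 mmHg | Type I error, r = 0.3 / 0.5 |
|---|---|---|---|
| 5% | 0.39 / 0.65 | 5% / 8% | 5.2% / 5.5% |
| 10% | 0.70 / 1.17 | 9% / 15% | 5.7% / 7.1% |
| 20% | 1.26 / 2.10 | 16% / 26% | 7.3% / 11.7% |

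Check on the last cell: the standard error is 12 × √(2/36) = 2.83 and 2.10 / 2.83 = 0.74. The normal approximation gives Φ(−1.22) + Φ(−2.70) = 0.111 + 0.003, or about 11.5%, close to the simulated value.

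Two milder cases: removing 15% from one arm and 5% from the other shifts the difference by 0.60–0.99 mmHg, with type I error 5.5–6.4%. Removing 10% from both arms gives no shift and about 5%.

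**Power cost of keeping every allocated patient.** If 1 of 36 PTG (precise therapy group) patients gains no benefit, the expected difference is 8 × 35/36 = 7.78 mmHg. If 2 do, it is 8 × 34/36 = 7.56 mmHg. With SD held at 12, exact t power falls from 79.7% to 77.4% and 75.0%.

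**The case against.** The strongest reply is that the text, read as a whole, already supports a sound order. The Arm information opens with patients who met the requirements and were randomised, the requirements include consent, the Brief Introduction ties inclusion to a signed form, and Section 6 then keeps everyone randomised. The unshown figure may set out exactly this sequence. This stands as far as it goes: the order is ambiguous, not shown to be reversed. It does not remove the point, because none of these sentences places the final eligibility decision or exclusion before the arm may be known.

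Patients do not know their group, so a patient's own refusal should not depend on it. That is fair. It confines selective consent to the staff who seek it, and does not prevent it.

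The untimed exclusion clause covers only the six not-eligible criteria, four of which are diagnoses. That also stands and narrows the room for discretion. Reachability is an inclusion criterion outside that clause, though its timing is equally unstated.

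Removing only the lowest scorers from one arm is a near worst case, and at 5% exclusion the effect on type I error is slight.

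Two stronger readings are tempting but unsupported. A reader might infer that admission triggers disclosure of the arm; the sentence sets only an earliest time. A reader might also compare the 100 list entries with "72 cases of patients are expected to be enrolled into this study" and infer an allowance for 28 losses after allocation. Spare numbers do not show that any loss is planned or has occurred, and the Brief Introduction speaks of more than 72 patients.

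**Conclusion.** The concern holds as a gap in the stated procedure and should be fixed. Following the readable rules as written, staff could exclude a patient or seek consent selectively when the arm may already be known, and an exclusion after list entry would contradict the intention-to-treat rule. The documents do not show that allocation precedes eligibility, that any patient was excluded in this way, or that anyone acted on knowledge of the arm.

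The size and direction of any bias are unknown. The illustrative range of about 0.4–2.1 mmHg, with type I error of about 5–12%, rests entirely on assumed one-sided exclusion of 5–20% and a correlation of 0.3–0.5. It vanishes if exclusion works equally in both arms. Confidence is medium, because the missing figure could settle the order.

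**What to change.** In Section 4, keep admission order as the queue and state the sequence:

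1. Signed consent and every inclusion and exclusion judgement are recorded, from information available in the same way for every patient.
2. The next concealed number is then drawn, from a sealed envelope or a list kept away from the surgical team.
3. Only then is the arm released to the surgeon.

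Add that every patient with a drawn number counts as randomised and stays in the intention-to-treat set, and that later ineligibility or no surgery is reported by arm. If the research-process figure already shows this order, repeat it in the text.

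The cost is protocol wording plus envelopes or a list holder outside the surgical team, with no extra patients or procedures. The downside is that a few patients found ineligible late remain in the analysis. With one or two such PTG patients gaining no benefit, the loss is about 2 to 5 percentage points of power (79.7% to 77.4–75.0%).

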Study Protocol

Official title:

**The Precise Surgical Treatment of Chronic Thromboembolic Pulmonary Hypertension:
Pulmonary Endarterectomy Guided by Three-dimensional Pulmonary Angiography**

Brief title

**Pulmonary Endarterectomy Guided by CT Scanning for Patients With Chronic
Thromboembolic Pulmonary Hypertension---PEACT**

Acronym:PEACT

Sponsor:Fuwai Hospital,Chinese Academy of Medical Sciences,Peking Union Medical College

Study types: interventional,Randomized single-blind controlled study

Document Date: 12/19/2018

Abbreviation and acronyms

CTEPH=chronic thromboembolic pulmonary hypertension;PEA=pulmonary endarterectomy;PAP=pulmonary artery pressure;PVR=pulmonary vascular resistance;PTG=precise therapy group;UCG=ultrasonic cardiogram;CPET=cardiac pulmonary exercise test;CT=computed tomography;RHC=right sided heart catheterization;WHO=World Health Organization;NT-pro BNP=N-terminal pro B-type natriuretic peptide.INR=international normalized ratio;6MWD=6 minutes walking distance; mmHg=millimeter mercury column;CF=coagulation factor;UCSD=University of California, San Diego;NOAC=new oral anticoagulant;3-D=Three-dimensional;

Brief Introduction of this study

This study is a randomized single-blinded controlled study to investigate the efficiency of 3-D pulmonary imagings, including 3-D pulmonary angiography and 3-D enhanced computed tomography, patients received PEA surgeries in our center was randomized into 2 groups, the PTG group (group 1) and traditional PEA therapy group (group 2), the peri-operative hemodynamic improvement and peri-operative prognosis such as peri-operative mortality and other severe complications were documented for both groups, and the follow-up result of UCG, CPET and RHC are compared for these 2 groups so as to investigate their long-term result after PEA surgeries. A total of more than 72 cases of patients with CTEPH are expected to be included into this study, with informed consent form signed, a longest 48 months follow-up result will be recorded, and the whole designed study is expected to end at the year 2022.

Catalog

1 Background.....	5
2 Objectives(Focus of the study).....	6
3 Design and Method.....	7
4 Eligibility/intervention information/Arm information.....	10
5 Outcome measures and time frame.....	12
6 Statistical Analysis Plan.....	13
7 Quality Control.....	14
8 Reference.....	15
9 Appendix.....	16
Sample of original medical record(1 patient).....	16

1 Background

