Sample size estimation was based on a hypothesis that the mean PAP of patients of PTG can be decreased by 8 mmHg more than that of the traditional group. Given the standard deviation of 12 mmHg was expected in the measurement of mean PAP, with a power of 80% and a significance statistically level of 5% on both side, a sample size of 36 of the PTG group was required.

2) Statistical Analysis:

The analysis was based on the principle of “Intention to Treat” (ITT). All randomized patients (regardless of whether they violate the protocol) will be included in the final analysis.

Continuous variables are presented as mean \pm standard deviation, unless otherwise specified. Significant differences were determined with the Mann-Whitney test or independent t-test according to the their distribution, Wilcoxon matched pairs signed rank test or paired t-test for the paired variables. Categorical variables were compared between the 2 groups using the chi-square test or Fisher exact test. Kaplan-Meier method was used to estimate survival, log-rank test was used to evaluate the survival difference between different groups.

The pulmonary occluded severity will be scored using CT scanning and pulmonary angiography for each patients, the scoring result will be compared with the hemodynamic result to investigate their possible correlations using Spearman Correlation Analysis.

All the statistical analysis were performed using SPSS version 22.0. P value less than 0.05 was considered statistically significant.

7 Quality Control

1) Data accuracy:

All the participants in this study are responsible for the data collection process, all the original medical document should be pictured or scanned as the evidence of recorded data; for parameters with possible subjective error, the original imaging or assessment profile should be saved, the parameters estimated by

2) Group coordination

Fuwai hospital was the largest cardiac surgery center in China and also one of the largest center in the world. Up to now, we had established a coordination team of CTEPH in our center, which consist of cardiac surgery department, pulmonary disease center, radiology department, intensive-care unit and ultra-sonic department, nuclear medicine department in our center.

All the imaging data had been evaluated by at least 2 professional staffs in that field, and the CT constructed imaging, pulmonary angiography imaging had been saved for re-assessment in case of possible subjective bias.

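### Section 5 gives four outcomes as the primary efficacy endpoint, Section 6 names haemodynamic improvement alone and sizes only mean PAP, and nothing says which result decides the trial

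*Combined protocol and SAP*

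**What the plan says.** Section 5 (Outcome measures and time frame) gives the primary endpoint for efficacy as "the peri-operative hemodynamic improvement, peri-operative mortality, major complications after surgery, and deaths in the follow-up period". A separate list of secondary endpoints follows. Mortality and complications are not in it.

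Section 6 (Statistical Analysis Plan) opens by stating that "the major endpoint is the hemodynamic improvement after the surgeries". Its sample-size paragraph deals with one variable: "Sample size estimation was based on a hypothesis that the mean PAP of patients of PTG can be decreased by 8 mmHg more" than in the traditional group, with SD 12 mmHg, 80% power, a two-sided 5% level and 36 patients in the PTG. Section 3 gives a total of 72.

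The analysis paragraph assigns methods by type of variable. Continuous variables get a t test or Mann-Whitney test. For events, "Categorical variables were compared between the 2 groups using the chi-square test or Fisher exact test", and for deaths over time the "log-rank test was used to evaluate the survival difference between different groups". None of these is labelled the primary analysis. One threshold covers them all: "P value less than 0.05 was considered statistically significant".

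Under the intention-to-treat principle, all randomised patients "will be included in the final analysis".

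**The concern.** The primary endpoint decides what the trial may conclude, and the plan states it twice in different terms. Suppose mean PAP shows no difference and major complications give P=0.04. Under Section 6 the trial has missed its endpoint. Under Section 5 an author could report a significant result on a primary outcome. Nothing written in advance would settle the matter, so the choice could be made after the data are seen.

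A second gap lies inside the first. Neither endpoint sentence names the haemodynamic variable. That it is mean PAP has to be inferred from the sample-size paragraph.

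**Working it through.** **1. Side by side**

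| Item | Section 5 | Section 6 |
|---|---|---|
| Outcomes given top status | Four | One |
| Haemodynamic variable named | No | Only in the sample-size paragraph (mean PAP) |
| Effect size and power | None | 8 mmHg, SD 12, 80%, for mean PAP only |
| Rule linking outcomes to success | None | None; P<0.05 throughout |

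No sentence says that Section 6 overrides Section 5, or that the four outcomes form a composite.

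**2. The plan's own figure**

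Inputs from Section 6: difference 8, SD 12, two-sided alpha 0.05, power 0.80. Equal allocation follows from the list of 50 and 50 in Section 4.

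n per arm = 2 × (1.960 + 0.842)² × (12/8)² = 2 × 7.85 × 2.25 = 35.3, so 36 per arm and 72 in total. The stated size reproduces.

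Power at 36 per arm: 8 / (12 × √(2/36)) = 2.828; 2.828 − 1.960 = 0.868; power 80.7%. The noncentral t with 70 df gives 79.7%. The t-based requirement is 36.3 per arm, an immaterial difference.

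**3. If any one of four unadjusted tests could carry the claim**

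For independent tests, family-wise error = 1 − Π(1 − size of each test).

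- All four at exactly 5%: 1 − 0.95⁴ = 18.5%. Whatever the dependence, four tests each at 5% cannot exceed 4 × 0.05 = 20%.
- With 36 per arm and uncommon events, Fisher and chi-square tests reject less often than 5%, so the figure depends on event rates. The documents give none. The null rates below, for peri-operative death / major complications / follow-up death, are assumptions.

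Exact test sizes at 36 per arm:

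| Event rate | Fisher | Chi-square if all expected counts ≥5, else Fisher |
|---|---|---|
| 2% | 0.01% | 0.01% |
| 5% | 0.29% | 0.30% |
| 10% | 1.38% | 2.02% |
| 20% | 2.58% | 4.71% |
| 40% | 2.57% | 4.94% |

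The log-rank test for follow-up death had a simulated size of 3.7% at 5% deaths and 5.0% at 20% deaths (exponential survival, censoring at 24 months, 40,000 runs each).

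Family-wise error, with mean PAP tested at 5%:

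| Tests for the three event outcomes | Rates 2/10/5% | Rates 10/40/20% |
|---|---|---|
| Fisher for all three | 6.6% | 11.1% |
| Chi-square/Fisher for all three | 7.2% | 15.7% |
| Fisher, with log-rank for follow-up death | 9.8% | 13.3% |
| Chi-square/Fisher, with log-rank for follow-up death | 10.4% | 15.9% |

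Lowest: 1 − 0.95 × 0.9999 × 0.9862 × 0.9971 = 6.6%. Highest: 1 − 0.95 × 0.9798 × 0.9506 × 0.950 = 15.9%. In round terms, 7% to 16%.

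**4. If four co-equal claims were kept with an equal split of alpha**

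Each test would be at 0.05/4 = 0.0125, critical value 2.498. Power for mean PAP at 36 per arm: 2.828 − 2.498 = 0.331, giving 63.0% (t test 60.6%). Restoring 80% needs 51 per arm (normal) or 52 (t test).

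**The case against.** The best defence is that Section 6 governs the analysis. It opens with a single endpoint and moves straight to a single hypothesis, while Section 5 merely lists the outcomes of main clinical interest. Section 3 also speaks of the endpoint in the singular. This is the natural reading, and under it the 5% level and the sample size both hold. But it is not written down. Section 5 uses the word primary, has its own secondary list, and leaves mortality and complications out of that list.

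A second defence is that Section 5, being singular and joined by a conjunction, means a composite. A continuous pressure change, binary events and deaths over time cannot be combined without a rule, and none is given.

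A third objection is well founded. A reader might infer that the trial runs at a false-positive rate of up to 18.5%. The documents do not support that. They nowhere say that one significant result out of four is enough, and the P<0.05 sentence is a general threshold, not a success rule. The 7% to 16% range also rests on assumed event rates and independence. The outcomes are probably positively correlated, which would generally lower the figures, and peri-operative deaths may be counted again among later deaths. The range shows what is at stake if the gap were used in that way. It does not estimate this trial's error rate.

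**Conclusion.** The contradiction stands and should be resolved, because the trial's conclusion rests on it. It is shown by the text alone and needs none of the assumed rates.

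Its size depends on which definition is meant. With mean PAP as the sole primary endpoint, error is 5% and power about 80% if all 36 per arm have a value. With an any-of-four rule, which the plan does not adopt, error would exceed 5% by an amount that cannot be fixed from the documents. A reader might also infer that the sample size is wrong. It is not: 36 per arm reproduces from the plan's own inputs, for mean PAP only.

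**What to change.** **Change Section 5 to match Section 6.** Name one primary endpoint: the between-arm difference in change in mean PAP, from the RHC immediately before PEA to the one immediately after. Section 3 already collects both measurements. The sponsor should confirm the variable and the time point, since both are inferred from the sample-size paragraph and from Section 5's reference to the peri-operative period. The Brief Introduction fits this reading. It records "the peri-operative hemodynamic improvement and peri-operative prognosis such as peri-operative mortality and other severe complications" for both groups and treats RHC at follow-up as part of the long-term result.

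**Reclassify the other three outcomes.** List peri-operative mortality, major complications and follow-up death as secondary or safety outcomes with 95% confidence intervals. Alternatively, test them in a stated fixed order after mean PAP, each only if the one before is significant.

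**Cover missing primary values.** State how randomised patients with no post-PEA RHC value, including those who die before it is taken, enter the primary analysis. With death no longer in the primary endpoint, the intention-to-treat statement alone does not answer this.

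**Cost.** Wording in Sections 5 and 6 and a decision on missing values, ideally made before the arms are compared. No new data are needed and 36 per arm is unchanged. The sponsor gives up stand-alone primary claims on mortality and complications, for which the trial was never sized. Keeping four co-equal claims by an equal alpha split would instead mean about 61% to 63% power for mean PAP, or 51 to 52 patients per arm.

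### The secondary cost endpoint starts only at follow-up, so it omits the index admission, where the arms differ by design, and it has no common time horizon

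*Combined protocol and SAP*

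**What the plan says.** Section 5 (Outcome measures and time frame) ends its list of secondary endpoints with "disease directly associated cost (average cost) in the follow-up period". It does not list the cost items, the data source, the denominator of the average or the length of the window.

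Section 3, part 2 (Clinical data collection process) divides the study into four periods:

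- The first covers the work-up: "Pre-operative period: From admission to the moment before surgeries".
- The second covers the surgery itself: "Operation period: The RHC result immediately before and after PEA surgeries are documented".
- The third is the rest of the hospital stay, from surgery until the patient goes home, with its own imaging checks.
- The fourth comes after that and is set by a visit schedule: "Follow-up period: A routine 3-, 6-, 12-, 24 months follow-up will be done".

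The Brief Introduction adds that "a longest 48 months follow-up result will be recorded" and expects the study to end in 2022.

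On the intervention, section 4 states that "Precised analyzed CT scanning and pulmonary angiography will be done for the patients in the precise therapy group" and describes group 1 as "precise PEA therapy with the guide of 3-D imaging techniques".

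Section 6 applies intention to treat to all randomised patients and compares continuous variables by t-test or Mann-Whitney test. It has no provision specific to cost.

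**The concern.** The trial compares two ways of planning and carrying out one operation. Whatever extra resource the precise strategy uses is spent before and during surgery. Some of what it might save, such as complications treated before discharge, would also fall in the index stay. A cost endpoint that opens only at follow-up sees neither. One of the trial's objectives is to promote 3-D imaging and set up a standard strategy around it, so a reader could easily take a follow-up cost result as the cost of that strategy.

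There is a second, smaller difficulty. Patients are observed for different lengths of time, and no horizon is fixed. An average of accumulated cost then depends partly on how long each patient was watched, and the plan does not say how a patient who dies or drops out enters the average.

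**Working it through.** **1. The plan's own figure.** The only calculation in the plan is the sample size in section 6: difference 8 mmHg, SD 12 mmHg, 80% power, two-sided 5%. The formula n per arm = 2 × (1.960 + 0.842)² × 12² / 8² gives 35.3, rounded up to 36, which agrees with the plan. Power at 36 per arm is 0.807 (normal approximation) or 0.797 (t distribution). Nothing below changes this; it only supplies the 36.

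**2. Cost window against study periods.**

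| Period (section 3) | Resource that may differ by arm | In the cost window? |
|---|---|---|
| Pre-operative | 3-D imaging analysis | No |
| Operation | Guided versus traditional procedure | No |
| Post-operative, before discharge | In-hospital complications, length of stay | No |
| Follow-up (visits at 3, 6, 12, 24 months) | Later care and repeat examinations | Yes |

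The same sentence of section 5 measures the change in CT score from baseline, so a wider window was used where one was wanted. No other section defines an index-admission cost. Repeat CT or angiography at follow-up could still be counted; the imaging that guides the operation is not.

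**3. Consequence for the arm contrast.** Let S be the saving in follow-up cost in group 1 and I the extra index-admission cost in group 1. The endpoint reports S; the net saving is S − I.

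- If I > S > 0, the endpoint shows a saving where there is a net cost.
- If I < 0, for example through fewer in-hospital complications, it understates the saving.

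The documents give neither S nor I, so neither sign nor size can be stated.

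**4. Unequal observation time.** A patient followed for 48 months has 48/24 = 2 times the accrual time of one followed for 24 months. Patients enter by admission date through a random list of 50 and 50, so calendar-driven follow-up has the same expected distribution in both arms. The inequality therefore adds variance. It becomes bias only if death or dropout differs by arm.

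**5. Deaths, as an illustration.** Assumptions, none of them in the documents: the average is total follow-up cost per randomised patient, monthly cost c is equal in both arms, the horizon is H months, and a peri-operative death has zero follow-up cost. An arm with peri-operative mortality p then has mean c × H × (1 − p).

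- One death in 36 lowers that arm's mean by 1/36 = 2.8%; four lower it by 4/36 = 11.1%.
- Mortality 10% versus 5%: 1 − 0.90/0.95 = 5.3% apparently cheaper in the higher-mortality arm.
- Mortality 10% versus 2%: 1 − 0.90/0.98 = 8.2%.
- Mortality 5% versus 5%: no distortion.

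H cancels, so these percentages are the same at 24 and 48 months. If cost were expressed per month alive, this distortion would vanish under the same assumptions. It would also vanish if survivors only were averaged, but that would no longer compare the randomised groups.

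**The case against.** None of the four objectives concerns cost. The endpoint is the last item in the secondary list and is openly labelled as follow-up cost, which is a legitimate downstream measure. The plan never says that it will report the cost of the strategy. This stands, and it keeps the point modest. It does not supply the missing index cost, a horizon or a denominator.

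The imaging increment may also be small. All patients have CT and pulmonary angiography before surgery, group 2 uses both in their traditional form, and CT and angiography scoring is planned for every patient. The documents do not say whether group 1 has extra scans or only more detailed analysis. This stands too, so group 1 cannot be assumed to be the costlier arm. Operation and complication costs remain outside the window in any case.

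Two stronger readings are tempting. A reader might infer that the endpoint makes early death look like a saving. That requires a total per randomised patient, which the intention-to-treat rule suggests but section 5 does not state, and it requires deaths to differ between arms. No mortality rate is given. Deaths are also a primary outcome with Kaplan-Meier and log-rank analysis, so an excess would be visible beside a low cost. If the Mann-Whitney test is used, a percentage shift in the mean is not the quantity tested.

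A reader might also infer that follow-up of up to 48 months biases the comparison. Under randomisation it is chiefly noise.

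**Conclusion.** The point about the window holds on the text alone: as the plan divides its periods, the cost endpoint excludes the whole index admission, where the strategies differ by design and where complications before discharge are treated. The endpoint as defined cannot show the net cost of the precise strategy. The direction of the error is unknown and its size cannot be computed from the documents.

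The point about the horizon holds in a limited form. A raw average over unequal follow-up mixes cost with time. That costs precision, and it introduces bias only if death or dropout differs between arms. The 2.8% per death rests on the assumptions listed above and describes one arm's mean; it becomes an arm difference only to the extent that deaths are unequal.

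This is a worthwhile, inexpensive improvement to a secondary endpoint. It does not touch the sample size or the haemodynamic comparison.

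**What to change.** Replace the cost item in section 5 with: total disease-related cost per randomised patient, from index admission (including the 3-D imaging work-up, the operation and the index stay) to one fixed horizon that all patients can reach.

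- **Horizon.** The 24-month visit is a natural choice if enrolment dates allow. With the study expected to end in 2022, patients operated on after 2020 would not reach it.
- **Deaths and dropout.** Keep patients who die in the average with the cost they accrued. State how patients lost before the horizon are handled.
- **Presentation.** Show index and follow-up cost separately beside the total, which preserves the figure now planned, and report cost next to mortality.
- **Definitions.** List the cost items and the data source.

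If only follow-up cost is kept, use a fixed window, name the denominator, and label the result as post-discharge cost, not as the cost of the strategy.

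The price is a few sentences in sections 5 and 6 and some extra extraction of index-stay charges. The documents do not describe a source for those charges, so their availability should be confirmed first. A fixed horizon also sets aside cost data collected beyond it; these can be reported descriptively.
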